## 5.7 Study Drug

---

Study drug will be taken orally QD, beginning on Day 1 (Baseline), and should be taken at approximately the same time each day, with or without food. Subjects will be instructed to return all drug containers (even if empty) to the study site personnel at each study visit; study site personnel will document compliance.

AbbVie will not supply any vitiligo disease-related concomitant medication therapy taken during the course of the study. AbbVie will supply upadacitinib and matching upadacitinib placebo.

Study drug will be packaged in quantities sufficient to accommodate the study design.

Each kit will be labeled per local requirements and this label must remain affixed to the kit. Upon receipt, study drug should be stored as specified on the label and kept in a secure location. Each kit will contain a unique kit number. This kit number is assigned to a subject via interactive response technology (IRT) and encodes the appropriate study drug to be dispensed at the subject's corresponding study visit. All blank spaces on the label will be completed by the site staff prior to dispensing to subjects. Study drug will only be used for the conduct of the study.

The individual study drug information is presented in [Table 2](#).

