**Table 2. Description of Study Drug**

Investigational Product	Mode of Administration	Dosage Form	Strength	Blinded or Open Label	Frequency	Manufacturer
Upadacitinib (ABT-494)	Oral	Extended-release, film-coated tablets	6 mg, 11 mg, or 22 mg	Blinded	QD	AbbVie
Placebo for upadacitinib (ABT-494)	Oral	Film-coated tablets	Not applicable	Blinded	QD	AbbVie

During the COVID-19 pandemic, study drug shipment can be made from the study site to the subject if allowed by local regulations. Refer to the operations manual for details on direct-to-patient shipment of study drug.

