## 7.2 Definition for Analysis Populations

---

The ITT Population includes all randomized subjects. Subjects will be included in the analysis based on treatment as randomized. The ITT Population will be used for all efficacy analyses.

The following populations will be used for the safety analysis:

- The Safety Population (Safety) is defined as all subjects who are randomized and received at least 1 dose of study drug in the study.
- The all upadacitinib treated (ALL\_UPA) Population is defined as all subjects who received at least 1 dose of upadacitinib in the study. This population will be used to provide a comprehensive summary of safety.

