2.2 Study Design Overview

This is a Phase 2, multicenter, randomized, double-blinded, parallel-group, placebo-controlled dose-ranging study that will evaluate the safety and efficacy of upadacitinib in adult subjects \geq 18 to 65 years of age with NSV. The study is comprised of a 35-day Screening Period, a 24-week double-blind treatment period (Period 1), a 28-week blinded long-term extension (Period 2), and a 30-day Follow-up Period.

Subjects who meet eligibility criteria at Baseline will be randomized in a 2:2:2:1:1 ratio to one of five treatment groups:

[figure not shown]
- Group 1: upadacitinib 22 mg once daily (QD) (N = 40) (Period 1) → upadacitinib 22 mg QD (Period 2)
- Group 2: upadacitinib 11 mg QD (N = 40) (Period 1) → upadacitinib 11mg QD (Period 2)
- Group 3: upadacitinib 6 mg QD (N = 40) (Period 1) → upadacitinib 6 mg QD (Period 2)
- Group 4: placebo (N = 20) (Period 1) → upadacitinib 22 mg QD (Period 2)
- Group 5: placebo (N = 20) (Period 1) → upadacitinib 11 mg QD (Period 2)

At Week 24, subjects who were randomized to placebo at Baseline will be switched to either upadacitinib 22 mg (Group 4) or upadacitinib 11 mg (Group 5) in a blinded fashion per pre-specified randomization assignments.

The AbbVie study team will be unblinded to perform the Week 24 primary analysis. The unblinding will take place after all subjects have completed the Week 24 visit or have prematurely discontinued prior to Week 24. Sites and subjects will remain blinded throughout the study.

The schematic of the study is shown in [Figure 1](#).

Figure 1. Study Schematic

BL = Baseline; F-VASI = Facial Vitiligo Area Scoring Index; PBO = placebo; QD = once daily; UPA = upadacitinib

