4.0 Analysis Populations

The following Intent-to-Treat (ITT) populations will be used for the analyses.

- The ITT Population in Period 1 (ITT_1) includes all randomized subjects in Period 1. Subjects will be included in the analysis according to the treatment groups that they are randomized to. Analyses will include the following 4 groups: upadacitinib (UPA) 22 mg QD, UPA 11 mg QD, UPA 6 mg QD and placebo.
- The ITT Population in Period 2 (ITT_2) includes all subjects entered Period 2. Subjects will be included in the analysis according to the 5 treatment groups that they are randomized to at baseline: UPA 22 mg QD-> UPA 22 mg QD, UPA 11 mg QD-> UPA 11 mg QD, UPA 6 mg QD-> UPA 6 mg QD, Placebo-> UPA 22 mg QD and Placebo-> UPA 11 mg QD.

- The ITT_1/ITT_2 Populations will be used for all efficacy analyses across Period 1/Period 2.

The following three Safety Populations will be used for the safety analysis:

- The Safety Population in Period 1 (Safety_1) is defined as all subjects who are randomized and received at least one dose of study drug in Period 1. Subjects will be summarized in the following 4 groups: UPA 22 mg QD, UPA 11 mg QD, UPA 6 mg QD and placebo, based on the treatment actually received (defined as the most frequent dose regimen received in Period 1).
- The Safety Population in Period 2 (Safety_2) is defined as all subjects received at least one dose of study drug in Period 2. Subjects will be included in the 5 groups same as which they were randomized to at baseline: UPA 22 mg QD-> UPA 22 mg QD, UPA 11 mg QD-> UPA 11 mg QD, UPA 6 mg QD-> UPA 6 mg QD, Placebo-> UPA 22 mg QD and Placebo-> UPA 11 mg QD.
- The all upadacitinib treated (ALL_UPA) Population is defined as subjects who received at least one dose of upadacitinib in the study. Subjects will be analyzed based on the treatment actually received: UPA 22 mg QD, UPA 11 mg QD and UPA 6 mg QD.

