6.0 Study Drug Duration and Compliance

For Safety_1/Safety_2 Population, duration of treatment will be summarized for each treatment group in Period 1 and Period 2. For ALL_UPA Population, duration of treatment will be summarized overall and for each upadacitinib dose group. Duration of treatment is defined as follows:

Period 1:

For subjects who did not continue into Period 2:

- Date of last dose of study drug in Period 1 – Date of first dose of study drug in Period 1 + 1.

For subjects who continued into Period 2:

- Minimum of (Date of first dose of study drug in Period 2 – Date of first dose of study drug in Period 1, Date of last dose of study drug in Period 1 – Date of first dose of study drug in Period 1 + 1.)

Period 2:

For subjects who continued into Period 2:

- Date of last dose of study drug in Period 2 – Date of first dose of study drug in Period 2 + 1.

ALL_UPA:

Study drug duration during the administration of study drug in ALL_UPA Population is defined as:

- Date of last dose of upadacitinib – Date of first dose of upadacitinib + 1.

Duration of treatment will be summarized using the number of subjects treated, mean, standard deviation, median, minimum and maximum. In addition, the number and percentage of subjects in each treatment duration interval (≥ 4 weeks, ≥ 12 weeks, ≥ 24 weeks, ≥ 36 weeks, ≥ 48 weeks) will be summarized for ALL_UPA Population.

Treatment compliance for Period 1 and 2 will be summarized by treatment groups for Safety Populations (Safety_1 and Safety_2). For ALL_UPA Population, treatment compliance will be summarized overall and for each upadacitinib dose group. Treatment compliance is defined as the number of tablets actually taken divided by the number of tablets that should have been taken. For subjects who prematurely discontinued the study drug, the planned tablets will only be counted prior to that scheduled visit of discontinuation. Percent compliance will be summarized.

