Non-Responder Imputation while incorporating Multiple Imputation (MI), NRI-MI, will be the primary approach to handle missing data for categorical endpoints in Period 1 (Section [9.2](#) and [Appendix E](#)).

- If there are missing data due to COVID-19 or any other missing data that can be reasonably assumed to be Missing at Random, a total of 30 datasets will be generated by PROC MI, and subjects will be characterized as responders or non-responders based on MI imputed values.
 - If not all the imputed datasets are identical, analysis will be performed as described in [Appendix E](#).
 - If all the 30 imputed datasets are identical, all statistical inferences will be calculated using the first imputed dataset: 1) The corresponding 95% CIs will be constructed based on normal approximation to the binomial distribution. 2) Adjusted differences, 95% CIs and p-values for the comparisons between each upadacitinib group and placebo will be calculated based on CMH test adjusting for stratification factors.
- If there are no missing data due to COVID-19 or any other missing data that can be reasonably assumed to be Missing at Random, the NRI-MI method will be the same as traditional NRI method. All statistical inferences will be calculated using the NRI imputed datasets.

For long-term efficacy, descriptive summary statistics including frequencies and percentages for categorical endpoints, along with 95% CIs based on normal approximation, will be provided based on as observed data.

Unless otherwise specified, any subject who is randomized based on a wrong stratum will be analyzed according to the actual stratum the subject belongs to.

"Baseline" refers to the last non-missing observation before the first administration of study drug or randomization if no study drug is given.

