10.3 Analysis of Laboratory Data

Data collected from central and local laboratories, including additional laboratory testing due to an SAE, will be used in all analyses, except for Baseline where SAE-related laboratory assessments on or before the first dose of study drug will be excluded. The clinical laboratory tests defined in the protocol operations manual (e.g., hematology and clinical chemistry) will be summarized.

Raw values and change from Baseline (percent change if applicable) to each applicable post-baseline visit will be summarized for selected laboratory variables in the Safety_1 and Safety_2 Populations. The following descriptive statistics will be presented by treatment groups: number of observations, Baseline mean (Standard deviation, SD), visit mean (SD), medium, change from Baseline mean (SD), standard error, and the 95% confidence interval of the mean change from Baseline.

Percent change from Baseline in LDL-C, HDL-C, total cholesterol and ratio of LDL-C to HDL-C will also be summarized similarly in the Safety_1 and Safety_2 Populations.

For the Safety_1 and ALL_UPA Populations:

A shift table from baseline to the worse post-baseline value (based on NCI CTC criteria) during treatment will be created. A similar shift table will be provided to summarize shifts from baseline to the final post-baseline value. The number and percentage of subjects will be summarized.

Laboratory abnormalities will be evaluated based on Potentially Clinically Important (PCI) criteria ([Appendix C](#)). For each laboratory PCI criterion, the number and percentage of subjects who have a laboratory value meeting the criteria will be summarized. Listings will be provided to summarize subject-level laboratory data for subjects meeting PCI criteria.

For the purpose of assessing for potential Hy's law cases, the frequencies and percentages of subjects with post-baseline liver specific function test values that meet PCI criteria ([Appendix C](#)) of potential clinical interest should be presented.

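### Read as written, the SAP's Baseline places placebo switchers' reference value about 24 weeks before upadacitinib in the ALL_UPA shift tables and vital-sign PCI counts

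*SAP*

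**What the plan says.** The SAP defines Baseline once, in 9.1 (General Considerations, under Efficacy Analyses): it "refers to the last non-missing observation before the first administration of study drug or randomization if no study drug is given". Section 10.1 neither repeats nor replaces this for safety. Section 10.3 touches on Baseline for laboratory data and uses the same anchor: all results are used "except for Baseline where SAE-related laboratory assessments on or before the first dose of study drug will be excluded". Section 10.4 and Appendix C refer to Baseline without defining it.

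Placebo counts as study drug. Protocol Table 2 lists it, and SAP 4.0 defines Safety_1 by a dose of study drug while giving that population a placebo column.

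ALL_UPA takes in anyone who receives upadacitinib, so Groups 4 and 5 enter it after the Week 24 switch. SAP 4.0 states: "Subjects will be analyzed based on the treatment actually received: UPA 22 mg QD, UPA 11 mg QD and UPA 6 mg QD". There is no separate column for switchers. Protocol 7.2 says of ALL_UPA: "This population will be used to provide a comprehensive summary of safety".

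For this same population the SAP moves the time origin elsewhere. Exposure in 6.0 is "Date of last dose of upadacitinib – Date of first dose of upadacitinib + 1", and 10.2.1 starts the adverse-event window at the first upadacitinib dose.

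The laboratory shift tables, laboratory PCI counts and vital-sign PCI counts are planned for Safety_1 and ALL_UPA only (10.3, 10.4). Table C-4 requires a change from Baseline for blood pressure, pulse and weight.

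**The concern.** One population carries two time origins. For a switcher, exposure and adverse events are counted from about Week 24, while laboratory and vital-sign change is measured from Day 1. A rise in blood pressure that occurred on placebo can then be counted in an upadacitinib column. A fall on placebo can offset a rise on upadacitinib, so that the rise is not counted.

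The switchers are unevenly spread. They enter the 11 mg and 22 mg columns and never the 6 mg column, in a study meant to compare doses.

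Safety_2 does show the switch groups separately, but its laboratory and vital-sign summaries are limited to raw values and change (or percent change) from Baseline. ALL_UPA is therefore the only planned shift or PCI tabulation that covers Period 2.

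**Working it through.** The plan gives no figure of its own on this point, and its sample-size statement does not enter. The inputs are the visit days in Protocol Appendix D, the group sizes in SAP 2.2 and the criteria in SAP Appendix C.

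**1. Distance between the two anchors.** Week 24 is Day 169, so 169 − 1 = 168 days, or 168/7 = 24 weeks.

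**2. Share of switchers in each ALL_UPA column.** Let d be the fraction of placebo subjects who leave before the switch. The documents give no value, so 0 to 30% is assumed. All 40 subjects randomised to each dose are taken to receive it. The share is 20(1 − d) / [40 + 20(1 − d)].

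| d (assumed) | 11 mg or 22 mg | 6 mg |
|---|---|---|
| 0 | 20/60 = 33% | 0/40 |
| 10% | 18/58 = 31% | 0/40 |
| 20% | 16/56 = 29% | 0/40 |
| 30% | 14/54 = 26% | 0/40 |

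**3. Part of a switcher's Baseline-to-visit interval spent on placebo.** Week 28: 24/28 = 86%. Week 36: 24/36 = 67%. Week 44: 24/44 = 55%. Week 52: 24/52 = 46%. These are calendar fractions, not estimates of bias.

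**4. How a classification can change.** The values are illustrative; the documents give no rates.

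- Systolic pressure, high criterion (at least 160 mmHg with a rise of at least 20): 138 before placebo, 152 at Week 24, 160 on upadacitinib. From Day 1, 160 − 138 = +22, which is counted. From the start of upadacitinib, 160 − 152 = +8, which is not.
- Weight, more than 7% gain: after +3% on placebo, a further gain above 1.07/1.03 − 1 = 3.9% is enough. After −3% on placebo, a gain above 1.07/0.97 − 1 = 10.3% is needed.
- Masking: −3% on placebo then +8% on upadacitinib gives 0.97 × 1.08 − 1 = +4.8% from Day 1. This is not counted, although the gain on drug exceeds 7%.

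**5. Which outputs depend on the anchor.**

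- Laboratory shift tables: yes, at any grade.
- Table C-4: yes, for every criterion.
- Tables C-1 and C-2: rarely. A value there must be Grade 3 or higher and at least one grade worse than Baseline. If both possible anchors are below Grade 3, the result is the same with either. Eligibility criterion 6 sets Screening limits clear of the PCI thresholds for all five haematology variables (for example haemoglobin at least 9 g/dL, against a PCI limit below 8) and for AST and ALT (at most 2 × ULN, against above 5 × ULN).
- Table C-3: no. Its criteria do not use Baseline.

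**The case against.** The strongest reply is that this is a gap in drafting, not a wrong rule. The definition sits in the efficacy section, and its fallback to randomisation suits an ITT population, since every safety population requires a dose. Moreover, SAP 6.0 introduces the ALL_UPA duration with the term study drug and then gives upadacitinib dates, so the authors may have meant the same for Baseline. Section 10.3 states an exclusion for SAE-related results and is not itself a definition.

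Part of this stands. The documents do not prove that the tables will be built from Day 1, and a reader who infers that they certainly will goes too far. But if 9.1 does not govern safety, the SAP has no safety Baseline at all and needs the same sentence. Where the SAP means upadacitinib in 6.0 and 10.2.1 it names it, and where it means a period's first dose in 7.3 it says so; 9.1 does neither.

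A second reply is that little is at stake: the tables are descriptive and PCI cases are listed by subject. That limits the consequence. The listings, however, cover only subjects who meet a criterion, so a switcher whose change is masked would not appear.

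The weight example has its own limits. Weight is in Table C-4 but not among the vital signs named in 10.4, and its Week 24 assessment cannot be confirmed from the schedule as extracted.

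A reader might also infer that placebo-period values will be counted as upadacitinib findings. The SAP does not say so. Grouping by treatment received (4.0) and limiting the worst-value shift table to the treatment period (10.3) point the other way. Still, no start date is written for the PCI counts or the final-value shift table.

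**Conclusion.** The point holds as a conflict of time origins on the plain reading of the SAP. ALL_UPA exposure and adverse events start at the first upadacitinib dose, while the only stated Baseline is about 24 weeks earlier for switchers. It affects the ALL_UPA laboratory shift tables and the Table C-4 counts for blood pressure, pulse and, where tabulated, weight. It concerns up to 33% of each of the 11 mg and 22 mg columns by plan (26% if 30% of placebo subjects leave before the switch, an assumed figure) and none of the 6 mg column.

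It would be tempting to conclude that the higher doses will look less safe, or that the safety results are biased by a known amount. The documents support neither. The error can go in both directions, and no rates of change on placebo are given, so neither its size nor its net direction can be estimated. Safety_1, and with it the placebo-controlled safety comparison, is unaffected. So are the efficacy analyses and every planned test. The point is worth correcting but does not threaten the trial's main conclusions.

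**What to change.** Add to SAP 10.1 that, for ALL_UPA shift and PCI tables and their listings, Baseline is the last available value before the first upadacitinib dose, and only values after that dose count as post-baseline. This aligns them with the ALL_UPA exposure and adverse-event rules. Keep the study Baseline for Safety_1 and Safety_2, where switchers have their own columns, and say in 10.1 that it applies there. State also whether weight is part of the vital-sign PCI tabulation, and correct the Appendix C introduction, which calls the vital-sign table C-3.

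The cost is one or two sentences and a second baseline flag in the laboratory and vital-sign datasets. Nothing changes for subjects randomised to upadacitinib. No new data are needed: laboratory and vital-sign assessments are scheduled at Week 24, and if weight was not taken then, the rule falls back to the latest weight before the switch.

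There is a small loss. Some switchers whose values meet a criterion relative to study entry, such as the systolic example at +22, will no longer be flagged in ALL_UPA. If the sponsor wants to keep that view, the listing can show the change from both anchors.

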9.2 Handling of Missing Data

In Period 1, missing data will be imputed using the following methods for the efficacy analyses:

- Mixed-Effect Model Repeat Measurement (MMRM): The repeated measures analysis will be conducted using a mixed model including observed

measurements at all visits. The mixed model includes treatment, visit and treatment-by-visit interaction, and stratification factors (age group [≤ 50 and > 50], Baseline disease severity [T-VASI < 15 and ≥ 15], and status of active vitiligo [Yes/No]) derived from actual values as fixed factors, and Baseline value as a covariate. An unstructured variance covariance matrix will be used. If the model cannot converge, an appropriate covariance structure matrix (e.g., autoregressive (1) or compound symmetry) will be used, and/or the stratification factor of age will not be included in the model. Parameter estimation is based on the assumption of data being missing at random and using the method of restrictive maximum likelihood (REML). MMRM will be the primary approach in the analysis of continuous variables in Period 1.

- Non-Responder Imputation while incorporating Multiple Imputation (MI) to handle missing data due to COVID-19 or any other missing data that can be reasonably assumed to be Missing at Random (NRI-MI): The NRI-MI will categorize any subject who does not have an evaluation during a pre-specified visit window (either due to missing assessment or due to early withdrawal from the study) as a non-responder for the visit. The only exceptions are: 1) when the subject is a responder both before and after the visit window in Period 1, the subject will be categorized as a responder for the visit. 2) missing data due to COVID-19 infection or logistical restriction or any other missing data that can be reasonably assumed to be Missing at Random will be handled by MI. The NRI-MI will be the primary approach in the analyses of categorical variables in Period 1. Random seeds are provided in [Appendix D](#) and more details are provided in [Appendix E](#). NRI-MI is the primary approach to handle missing data for categorical endpoints in Period 1.
- Multiple Imputation (MI): The MI approach will be used as a sensitivity analysis for the primary efficacy endpoint. Markov Chain Monte Carlo (MCMC) will be first applied to augment data into monotonic missing pattern and PROC MI will be used to generate 30 datasets using the regression method. The variables to be included in the imputation model are: treatment group, stratification factors (age group [≤ 50 and > 50], Baseline disease severity [T-VASI < 15 and ≥ 15], and status of active vitiligo [Yes/No]) derived from actual values, Baseline, and measurements at each visit up to the end of the Period 1. The random seed for MCMC and the random seed for

PROC MI are specified in [Appendix D](#). The imputed post-baseline measurements will be rounded to the same precision as the observed data. The imputed endpoint will be analyzed using each of the 30 datasets using ANCOVA for the primary endpoint. SAS PROC MIANALYZE will be used to generate the final inferences of the difference between upadacitinib group and placebo.

In Period 2, all values collected in the study will be used to summarize the long-term efficacy as observed (AO) in Period 2:

- The AO analysis will not impute values for missing evaluations, and thus a subject who does not have an evaluation at a scheduled visit will not be included in the AO analysis for that visit.

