## 7.4 Statistical Analyses for Efficacy

---

The efficacy analysis will be based on the ITT Population and all statistical tests will be performed at a 2-sided significance level of 0.1. The 95% confidence interval of the treatment effect will be provided.

- For continuous variables, comparisons of change and/or percent change from Baseline will be made between upadacitinib and placebo based on the Mixed Model Repeated Measures (MMRM) adjusting for treatment, visit, treatment-by-visit interaction, and stratification factors derived by the actual value (age group [ $\leq 50$  and  $> 50$ ], Baseline disease severity [T-VASI  $< 15$  and  $\geq 15$ ], and status of active vitiligo [Yes/No]) as fixed factors, and Baseline value as a covariate. The MMRM will be the primary approach to handle missing values for continuous endpoints.
- For categorical variables, comparisons will be made between upadacitinib and placebo using the Cochran-Mantel-Haenszel (CMH) test, adjusting for the stratification factors derived by the actual value: age group ( $\leq 50$  and  $> 50$ ), Baseline disease severity (T-VASI  $< 15$  and  $\geq 15$ ), and status of active vitiligo (Yes/No). Non-Responder Imputation incorporating multiple imputation (MI) to handle missing data due to COVID-19 (NRI-MI) will be the primary approach to handle missing values for categorical endpoints.

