2.4 Sample Size Determination

Assuming a Week 24 percent change from Baseline in F-VASI of 0% in the placebo arm, a conservative estimate based on a prior study in vitiligo,¹ the planned total sample size of 160 subjects (40 subjects in each upadacitinib group, 40 subjects in total in the placebo groups) will provide more than 90% power to detect the treatment difference of 40% reduction (assuming a standard deviation of 54.8%) in at least 1 upadacitinib group versus placebo using a 2-sided significance level of 0.1 based on the two-sample t-test.

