9.0 Efficacy Analyses

9.1 General Considerations

All efficacy analyses will be conducted in the ITT Population in each period (ITT_1 and ITT_2). All tests will be 2-sided at an alpha level of 0.1.

The Primary Analysis will be performed after all ongoing subjects have completed Week 24 or have prematurely discontinued prior to Week 24, data pertaining to Period 1 has been cleaned, and the database has been locked. This will be the only and final analysis for the efficacy endpoints in Period 1.

For analysis in Period 1, continuous endpoints and categorical endpoints will be analyzed using Mixed-Effect Model Repeat Measurement (MMRM) and Cochran-Mantel-Haenszel (CMH), respectively.

The analysis models and imputation methods for categorical and continuous endpoints in Period 1 and Period 2 are summarized in the following table:

Table 1. Analysis Models and Imputation Methods

Period	Type of Variables	Imputation Method	Intercurrent Events Handling	Analysis Model
Period 1	Continuous	MMRM ^a	The treatment policy strategy is used in this study. Under this strategy, all values for the variable of interest are used regardless of the intercurrent event.	MMRM model includes treatment, visit and treatment by visit interaction, stratification factors (age group [≤ 50 and > 50] ^e , baseline disease severity [T-VASI < 15 and ≥ 15] ^d , and status of active vitiligo [Yes/No]), and baseline measurement
	Categorical	NRI-MI ^b	The treatment policy strategy is used in this study. Under this strategy, all values for the variable of interest are used regardless of the intercurrent event.	CMH test adjusting for stratification factors (age group [≤ 50 and > 50], baseline disease severity [T-VASI < 15 and ≥ 15], and status of active vitiligo [Yes/No])
Period 2	Continuous	AO ^c	The treatment policy strategy is used in this study. Under this strategy, all values for the variable of interest are used regardless of the intercurrent event.	ANCOVA includes treatment, stratification factors (age group [≤ 50 and > 50], baseline disease severity [T-VASI < 15 and ≥ 15] ^d , and status of active vitiligo [Yes/No]), and baseline measurement
	Categorical	AO ^c	The treatment policy strategy is used in this study. Under this strategy, all values for the variable of interest are used regardless of the intercurrent event.	Descriptive summary

CMH = Cochran-Mantel-Haenszel; ANCOVA = Analysis of Covariance

- Mixed-Effect Model Repeat Measurement.

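### The Period 1 MMRM allows only one baseline slope for Weeks 2 to 24; if the slope changes over visits, some or all of the Week 24 precision gain from baseline adjustment may be lost

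*SAP*

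**What the plan says.** SAP 9.1, Table 1, gives the terms for continuous Period 1 endpoints: "MMRM model includes treatment, visit and treatment by visit interaction", followed by the three stratification factors and the baseline measurement. SAP 9.2 repeats the list, with the factors "as fixed factors, and Baseline value as a covariate", and specifies an unstructured covariance matrix. Protocol 7.4 has the same terms, ending "and Baseline value as a covariate". Treatment is the only term that interacts with visit.

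The F-VASI visits in Period 1 are Weeks 2, 4, 8, 12, 18 and 24 (Protocol Appendix D; sample code in SAP Appendix E).

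The sample size in SAP 2.4 claims "more than 90% power to detect the treatment difference of 40% reduction", "using a 2-sided significance level of 0.1 based on the two-sample t-test". It takes no credit for baseline adjustment.

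**The concern.** The endpoint is percent change from baseline. It is zero at baseline by construction and develops over 24 weeks, so a baseline association that is weak at Week 2 and stronger at Week 24 is plausible. A model with one slope must compromise between visits. Under an unstructured covariance it gives most weight to the visits with the smallest residual variance. If variability grows over time, those are the early visits, and the slope applied at Week 24 can be far from the Week 24 slope.

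What is at stake is mainly the standard error of the primary contrast. A secondary issue is missing data. MMRM is the primary method for handling it, and Protocol 5.6 describes only a discontinuation visit and a 30-day follow-up after study drug is stopped, so some Week 24 values may be absent. A wrong slope could then affect the estimate as well.

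The MMRM also differs from other models in the SAP. The Period 2 ANCOVA is fitted by visit, and the imputation regressions take each visit in sequence on baseline and the preceding visits. Both let the baseline coefficient differ by visit.

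**Working it through.** **1. The plan's own figure.** Inputs from SAP 2.4: "Assuming a Week 24 percent change from Baseline in F-VASI of 0% in the placebo arm"; a 40-point difference; "assuming a standard deviation of 54.8" (percentage points); "40 subjects in each upadacitinib group, 40 subjects in total in the placebo groups"; two-sided alpha 0.1.

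- Standard error = 54.8 × √(2/40) = 12.25.
- Difference / standard error = 40 / 12.25 = 3.264.
- Power (normal) = Φ(3.264 − 1.645) = 94.7%. The exact t-test value is 94.4%.

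The claim of more than 90% reproduces with no covariate in the calculation.

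**2. What one slope does at Week 24.** With treatment-by-visit in the model and complete data, the Week 24 estimate is the difference in Week 24 means minus slope × the difference in baseline means. Let ρ be the within-arm correlation of baseline F-VASI with Week 24 percent change, b the vector of true visit slopes per SD of baseline (Week 24 value b24 = ρ × 54.8), and S the residual covariance.

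- The common slope tends to 1′S⁻¹b / 1′S⁻¹1. Call its ratio to b24 k.
- Variance relative to no adjustment is 1 − ρ² with a visit-specific slope, and (1 − ρ²) + (1 − k)²ρ² with the common slope.
- Standard error, common slope relative to visit-specific = √[1 + (1 − k)² ρ² / (1 − ρ²)].

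**3. Numbers.** The documents give only the Week 24 SD. The values of ρ, the slope path and the covariance pattern below are assumptions. Slopes grow from near zero to b24 either linearly in time or with its square root.

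| Assumed covariance | Slope path | k | SE ratio, ρ = 0.3 | SE ratio, ρ = 0.45 |
|---|---|---|---|---|
| Any of these | Constant | 1.00 | 1.000 | 1.000 |
| SD rising with √time, random-walk correlation | Square root | 0.29 | 1.025 | 1.062 |
| Same | Linear | 0.08 | 1.041 | 1.102 |
| SD rising from 45% to 100% of 54.8, equal correlation 0.6 | Square root | 0.21 | 1.031 | 1.077 |
| Same | Linear | −0.06 | 1.054 | 1.134 |
| Constant SD, equal correlation 0.6 | Square root | 0.64 | 1.006 | 1.016 |
| Same | Linear | 0.47 | 1.014 | 1.035 |

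Example, ρ = 0.45 and k = 0.08: 0.92² × 0.2025 / 0.7975 = 0.215, and √1.215 = 1.102.

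The random-walk rows give the range of about 3% to 10%. The other two patterns widen it to about 1% to 13%.

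**4. Simulation check, complete data.** Common against visit-specific slope, Week 24 standard error:

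- Linear growth: 12.3 against 11.8 at ρ = 0.3 (ratio 1.04); 12.1 against 10.9 at ρ = 0.45 (1.11 from the rounded figures).
- Square-root growth: 12.0 against 11.7 (1.03); 11.7 against 11.0 (1.06).
- Constant slope: no gain from the interaction.

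In 4,000 simulated trials per setting (4 arms of 40, true difference −40, ρ of 0.3 or 0.5), the mean estimate lay between −39.8 and −40.4 for the unadjusted, common-slope and visit-specific analyses alike.

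**5. Power of the planned model.** At ρ = 0.3 with linear growth it is 94.2% to 95.6%, against 94.4% unadjusted and 96.0% with visit-specific slopes. At ρ = 0.5 with linear growth it is 93.8% to 97.3%. The lowest value in the grid examined was 88.6%, at ρ = 0.5 with a slope that changes sign between early and late visits and equal correlation with rising SD.

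**6. Missing data.** When dropout depended on baseline equally in all arms, the simulated comparison stayed unbiased. A deliberately adverse pattern was also tried: after Week 8 about 23% of placebo subjects with high baseline and about 13% of one active arm with low baseline drop out, with a linearly growing slope. Against a true −40 the common slope gave −34.1 to −35.4 at ρ = 0.3, and −31.4 to −34.2 at ρ = 0.5. With the interaction the estimates were −39.1 to −40.3 (Monte Carlo error about 0.9). Nothing in the documents predicts this dropout pattern.

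**7. Cost if the term is not needed.** With a constant slope at ρ = 0.3 the standard error went from 11.57 to 11.60 (0.3%). With no baseline effect it rose 0.7% in one simulation and was unchanged in another.

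**The case against.** The strongest reply is that a main-effect covariate is a valid prespecified choice and the loss is hypothetical. The endpoint is already scaled to each subject's baseline, so a material baseline slope cannot be presumed, and the documents give neither ρ nor the slope's course. That stands, and it is why the point is conditional.

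It is also fair that no planned inference depends on the gain. At ρ of 0.2 to 0.3, visit-specific slopes add only about 0.7 to 1.6 power points over no adjustment at all (95.1% and 96.0% against 94.4%).

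A reader might infer three stronger things that the documents do not support:

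- **That the Week 24 comparison gets little benefit from baseline.** The planned model keeps the whole gain if the slope is constant, and 37% to 87% of it under square-root growth in the patterns examined. Only steeper growth or a sign change removes most or all of it.
- **That the primary estimate is biased.** It is not with complete data. In the missing-data checks, bias appeared only when dropout depended on baseline differently by arm.
- **That the MMRM and the MI sensitivity analysis certainly adjust differently.** SAP 9.2 does not list the covariates of the ANCOVA that follows imputation. If baseline is among them, its slope is specific to Week 24, but the text does not say so.

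What the reply does not supply is a reason to assume a constant slope. The SAP gives none.

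**Conclusion.** The point holds as a low-priority efficiency improvement. The model as written imposes one baseline slope on six visits. If the true slope grows over visits and ρ is 0.3 to 0.45, the Week 24 standard error is about 3% to 10% larger than it needs to be. The size depends on the assumed covariance, and the loss is nil if the slope is constant.

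The stated power above 90% stands, because it was derived without the covariate. Only the most adverse assumed case, with a slope that changes sign, took the planned model below 90%. Bias under MAR is a concern only if dropout depends on baseline in different ways across arms, which is possible but not indicated.

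**What to change.** Add the baseline-by-visit interaction to the MMRM in SAP 9.1, Table 1, and SAP 9.2 for percent change in F-VASI, and align Protocol 7.4. For consistency, do the same for the other continuous Period 1 endpoints measured at several visits. State that the term is kept in the non-convergence fallback, which now simplifies the covariance and/or drops the age factor. Make the change before the Week 24 unblinding.

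The cost is one parameter per additional visit: 5 for F-VASI, and fewer for endpoints with fewer visits, such as VitiQoL. No new data are needed. If the interaction proves unnecessary, the standard error rises by about 1% or less.

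In the same edit, list the covariates of the MI ANCOVA. A difference between the two analyses can then be attributed to missing-data handling and not to baseline adjustment.
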